## Study Design

40 healthy male and female subjects age 18-60 yr will be recruited for this study (BMI 28-40). Exclusion criteria include any clinically significant medical condition, including diabetes, uncontrolled hypertension, heart disease, bleeding disorder, kidney or liver dysfunction, neurologic disease, psychiatric or eating disorders; use of tobacco or opiates or history of alcohol or drug abuse; recent weight change  $\pm 5\%$ ; or medications that affect body weight. Subjects will have a physical examination and screening blood studies, including fasting glucose levels, comprehensive metabolic panel and CBC. An EKG will also be performed.

Subjects will be recruited for a 5-week crossover study with lorcaserin (LOR) and placebo followed by treatment with LOR or placebo for 24 weeks. **Phase 1:** Participants will be randomized to receive either LOR (10 mg bid) or placebo for 7 days followed by a 3 week washout period and will then be crossed over to receive 7 days of the other treatment (LOR or placebo). Thus each subject will be studied twice: once after receiving placebo and again after receiving lorcaserin. *Subjects will continue on a weight maintenance diet during this time to remain weight stable.* Salivary cortisol levels will be obtained at 0800h and at 2300h on days 2 and 6 of placebo and LOR. A 24h urine will be collected on day 6 of placebo and day 6 of LOR. On day 7 of both the placebo and LOR treatments, subjects will be studied in the clinical research center in the morning after an overnight fast. A lumbar puncture (spinal tap) will be performed and blood samples will be obtained. Subjects will then be fed a standardized breakfast (300 kcal). A laboratory test meal will be performed 4h later as described below. **Phase 2:** After completing the 7-day placebo and LOR studies, subjects will then be treated with LOR 10 mg bid (n= 40) for 24 weeks (Fig. 1). *Subjects will receive nutritional counseling to reduce their daily caloric intake to 600 kcal below their calculated caloric requirement and will be encourage to exercise moderately for 30 min daily.* Subjects will visit the clinic monthly during the 24 week study period for monitoring of vital signs and food counseling which will include review of food diaries. Salivary cortisol levels will be obtained the night before the monthly visits. Blood will be obtained at months 1, 2, 4 and 6 for safety monitoring and protein and hormone level analysis. At the end of the 24 week period subjects will be admitted to the GCRC for an LP followed by a fixed breakfast and a laboratory test meal 4h later. CSF will be tested for various proteins and hormones. Subjects will collect a 24h urine beginning the day before this final LP.

**Lumbar Puncture:** LP will be performed after an overnight fast by [name], Professor of Anesthesia and Director of Obstetrical Anesthesia, using a 25G Whitacre needle. 12 ml of CSF (approximately 2 teaspoons) will be removed at each LP.

**Laboratory Meal:** Subjects will be studied in the Eating Behavior Lab under the supervision of [name]. Subjects will be fed a standardized breakfast (300 kcal). A multiple-item test meal consisting of a fixed buffet will be performed 4h later. Subjects will be seated at a table in front of a food array and told to eat as much as they like over a 1h period. Hunger and satiety will be assessed using a visual analog scale. Food energy and macronutrient consumption will be calculated using the Nutrient Data Systems software program.

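### The protocol text provided enrols women aged 18-60 but names no pregnancy or lactation exclusion, no pregnancy test and no rule for data collected during a pregnancy

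*Combined protocol and SAP*

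**What the plan says.** Study Design sets the population as "40 healthy male and female subjects age 18-60 yr will be recruited for this study (BMI 28-40"). The Scientific Abstract gives a different number (60) and BMI ceiling (42), but the same ages and both sexes, so that discrepancy does not affect this point.

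The exclusions begin "Exclusion criteria include any clinically significant medical condition, including diabetes, uncontrolled hypertension, heart disease, bleeding disorder, kidney or liver dysfunction". They go on to neurologic, psychiatric and eating disorders, tobacco, opiates, alcohol or drug abuse and recent weight change, and end with "or medications that affect body weight". On screening, the section says "Subjects will have a physical examination and screening blood studies, including fasting glucose levels, comprehensive metabolic panel and CBC", and adds an EKG.

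Phase 1 gives each treatment "for 7 days followed by a 3 week washout period and will then be crossed over to receive 7 days of the other treatment", and on diet it says "Subjects will continue on a weight maintenance diet during this time to remain weight stable". In Phase 2 participants take lorcaserin for 24 weeks, and "Subjects will receive nutritional counseling to reduce their daily caloric intake to 600 kcal below their calculated caloric requirement". A lumbar puncture is done at the end of each Phase 1 period and again at week 24.

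Data and Safety Monitoring adds CBC and metabolic panels during the study. Statistical Procedures plans a multiple regression predicting Phase 2 weight loss from Phase 1 test-meal and CSF POMC results, together with correlations involving leptin, insulin and HOMA-IR, in about 32 completers.

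**The concern.** Eligibility covers women of childbearing age, yet none of the named criteria or tests is aimed at pregnancy. A healthy woman in unrecognised early pregnancy could meet every listed criterion and pass every listed test. She would then receive the drug, the lumbar punctures and the calorie deficit. That is an avoidable risk to mother and fetus in a study whose own safety section describes it as low risk.

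There is also an analysis problem. The 24-week weight change is the outcome that the study is built to predict. Pregnancy changes weight for reasons unrelated to the drug, and it could also change food intake, leptin, insulin and cortisol. With about 32 completers, one such participant can influence a regression or correlation, and the plan does not say how her data would be treated.

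**Working it through.** **The plan's own figure.** Statistical Procedures recruits 40 to retain 32 after 20% dropout: 32 / (1 - 0.20) = 40. This reproduces and is not in dispute.

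**Exposure** (Study Design):
- Whole study: 1 + 3 + 1 + 24 = 29 weeks.
- On lorcaserin: 1 + 24 = 25 weeks. This takes Phase 2 as lorcaserin for all 40, as the Phase 2 paragraph says; the sentence introducing the design says "Subjects will be recruited for a 5-week crossover study with lorcaserin (LOR) and placebo followed by treatment with LOR or placebo for 24 weeks".
- On placebo: 1 week. Off drug (washout): 3 weeks.
- At a calorie deficit: 24 weeks. Phase 1 is on weight maintenance.
- Lumbar punctures: 2 + 1 = 3 at most.

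**What the named provisions would detect:**

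| Provision | Section | Aimed at pregnancy? |
|---|---|---|
| Listed medical, neurologic, psychiatric and eating disorders | Study Design | No |
| Tobacco, opiates, substance abuse, weight-active drugs | Study Design | No |
| Recent weight change of 5% | Study Design | No; early pregnancy need not produce it |
| Physical examination, glucose, metabolic panel, CBC, EKG | Study Design | No pregnancy test named |
| CBC and metabolic panels on study | Data and Safety Monitoring | No |
| Rule for data during a pregnancy | Statistical Procedures | None stated |

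The only related word anywhere is part of the job title of the person doing the lumbar punctures.

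**Effect of one affected participant (illustration, assumed values).** Take 31 unaffected completers with true r = 0.50 and outcome SD of 1, so the outcome sum of squares is 30. Add one participant with an average predictor value whose weight change lies 3 SD from the mean. The outcome sum of squares rises by 9 x 31/32 = 8.7; the cross-product and the predictor sum of squares do not change. Then r = 0.50 / sqrt(1 + 8.7/30) = 0.50 / sqrt(1.29) = 0.44.

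**Cost in precision of leaving her out.** The smallest correlation detectable with 80% power at two-sided 5% is tanh[(1.96 + 0.84) / sqrt(n - 3)]. This gives 0.478 at n = 32 and 0.485 at n = 31. Exclusion costs almost nothing, and no change to the sample size is needed.

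**Frequency (assumed inputs only).** If half of the 40 are women, and half to three quarters of those are of childbearing potential, there are 10 to 15 such women. At an assumed 1-5% risk of conceiving over 29 weeks, 10 x 0.01 = 0.10 to 15 x 0.05 = 0.75 pregnancies would be expected. The documents give neither the sex split nor the risk. This range counts conceptions during the study, not women already pregnant at screening.

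**The case against.** The strongest reply is that silence in this text proves little. Some material was removed before review. Data and Safety Monitoring refers back to an outline of the headache risk that is not in the supplied text, so at least one risk section is missing, and a pregnancy provision could sit there. The exclusion and blood-test lists are also worded as open lists. This stands as a limit: the supportable statement concerns the text provided, and a reader should not infer that the trial had no pregnancy provision at all. It does not dispose of the point. The eligibility and screening paragraph was supplied and is where such a provision belongs, and a criterion that is not written down cannot be applied consistently.

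A second reply is that monthly visits, adverse-effect checks at every visit and 24-hour reporting of unanticipated events would bring a pregnancy to light. They might, later on. They are not tests for pregnancy and do not act before the first dose.

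Three stronger readings are tempting and not supported:
- A reader might take the 29 weeks as time on drug and diet. It is whole-study duration and includes a 3-week washout and a weight-maintenance phase.
- A reader might infer that a pregnant woman's data would be kept. The plan neither keeps nor removes them.
- A reader might treat the 0.10-0.75 range as an estimate for this trial. Every input is assumed, and a woman found to be pregnant might not complete, which weakens the regression argument further.

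**Conclusion.** The concern holds for the protocol text provided. The named exclusions, screening tests and on-study laboratory tests would not identify an early pregnancy, and the analysis section has no rule for data collected during one. The consequence for an affected woman is up to 25 weeks on lorcaserin, 24 weeks at a 600 kcal/day deficit and three lumbar punctures. These are maxima that assume the pregnancy goes unnoticed throughout and Phase 2 is lorcaserin.

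The statistical effect is modest and conditional: under the assumed values above, one participant moves a correlation of 0.50 to 0.44. The main reason to act is safety, and protecting the 24-week weight outcome is secondary. Confidence is medium because a provision may exist in a section not supplied.

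**What to change.** 1. In Study Design, add pregnancy and breastfeeding to the exclusions, and add hCG to the screening tests for women of childbearing potential. This can apply only to subjects not yet dosed. Statistical Procedures shows that at least 10 + 10 = 20 have already completed Phase 1, so at most 20 of the planned 40 remain. Leave contraception requirements and the timing of any repeat tests to the investigator and the IRB.
2. In Statistical Procedures, state that weight, food-intake and hormone data from the onset of any pregnancy are left out of the Phase 2 weight-loss prediction and correlation analyses. This covers pregnancies that begin after screening, which the screening test cannot catch, and can apply to everyone, including subjects already dosed.
3. If equivalent provisions exist in a section not supplied, cross-reference them in Study Design instead.

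The cost is a short amendment and one inexpensive test on blood already drawn. The downside is that a few women become ineligible. The sample size does not change.

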### **Scientific Abstract**

The overall objectives of this study are to validate biomarkers that can be used to predict responses to the weight loss medication, lorcaserin, and to characterize counterregulatory responses to drug therapy that may limit efficacy. Studies will focus on the hypothalamic melanocortin (MC) system, including the proopiomelanocortin (POMC)-derived MSH peptides, the MSH antagonist, agouti related protein (AgRP) and brain MC-Rs, which are key mediators of the central response to weight loss. Lorcaserin is a serotonin (5HT2cR) agonist that works primarily by activation of POMC neurons and melanocortin signaling. We have found that measurements of the POMC prohormone in cerebrospinal fluid (CSF) can serve as a marker of central POMC activity in humans; plasma AgRP measurements have also emerged as a potential biomarker of brain AgRP activity. The current protocol will examine the acute (1 wk) effects of lorcaserin vs placebo on these biomarkers and on feeding behavior, in response to a laboratory test meal, as predictors of the longer-term (24-wk) response to lorcaserin. Counterregulatory mechanisms that may limit the effectiveness of lorcaserin treatment will also be characterized with a focus on the hypothalamic-pituitary-adrenal (HPA) axis and changes in AgRP levels. 60 healthy male and female subjects age 18-60 yr (BMI 28-42) will be recruited for a 5-wk double-blind crossover study with lorcaserin and placebo followed by treatment with lorcaserin or placebo for 24 wks. Participants will be randomized to receive either lorcaserin or placebo for 7 days followed by a 3 wk washout period and will then be crossed over to receive 7 days of the other treatment. On day 7 of both the placebo and lorcaserin treatments, subjects will be studied in the morning after an overnight fast in the clinical research center. A lumbar puncture (LP) will be performed to obtain CSF and blood samples will be obtained. Subjects will then be fed a standardized breakfast (300 kcal). A laboratory test meal will be performed 4h later. After completing the 7 day placebo and lorcaserin studies, subjects will then be continued on lorcaserin (n= 40) for 24 wks. Subjects will receive nutritional counseling to reduce their daily caloric intake to 600 kcal below their calculated caloric requirement and will be encouraged to exercise moderately for 30 min daily. Subjects will visit the clinic monthly during the 24 wk study period for counseling and to review food diaries; vital signs and safety labs will be monitored. Blood will be obtained for AgRP and hormone levels. At the end of the 24 wk period subjects will be admitted to the clinical research center for an LP followed by a

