### **Statistical Procedures**

40 subjects will be recruited to account for a predicted 20% dropout rate in order to retain 32 subjects. For phase 1, the primary outcome is difference in food intake after 7 days of drug compared to placebo. Based on known acute changes in food intake after LOR a sample size of 24 subjects would be required using paired analysis (10). This sample size is more than adequate if CSF POMC is used as the primary outcome variable using a SD of 59 fmol/m (for overweight and obese subjects) to detect a 20% change in CSF POMC as has been reported for hypothalamic POMC in animals after treatment with 5-HT2cR agonists (23). However in order to use the outcomes of phase 1 to predict phase 2 wt loss, 40 subjects will be recruited to retain 32 and to achieve a range of wt loss as predicted by clinical trials (9). Food intake, including food energy and macronutrient consumption will be correlated with baseline POMC and AgRP levels. Differences in food intake at the placebo and LOR test meals will be correlated with changes in melanocortin peptide levels as well as with wt loss after 24 wks. Multiple regression modeling will be used to predict phase 2 wt loss in the LOR-treated participants from the within-subject difference between LOR and placebo test meal results and CSF POMC measurements from Phase 1. Bivariate Pearson correlation coefficients will be determined and stepwise multiple regression analyses will be performed to detect associations between POMC and AgRP and changes in levels following LOR and placebo with relevant variables: wt change, food intake, adiposity, leptin, sOB-R, insulin, HOMA-IR, gut hormones. Phase 1 is a double-blind trial with lorcaserin and placebo. After 10 subjects completed phase 1 the investigators were unblinded to the treatment of those 10 subjects in order to perform an interim analysis on the neuropeptide changes. We did detect a significant change in CSF POMC levels in the first 10 subjects but changes were not significant for other POMC derived peptide values. We would now like to unblind the next 10 subjects who have completed phase 1 in order to perform an interim analysis on the first 20 subjects as this may help with determining if we need additional POMC-derived study markers and optimization of assay conditions. The double blind will then continue for the subsequent study subjects.

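### The two crossover sequences enter Phase 2 with different times off lorcaserin, and the weight-loss model has no sequence term or stated baseline weight

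*Combined protocol and SAP*

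**What the plan says.** The Study Design section describes the first Phase 1 treatment as given "for 7 days followed by a 3 week washout period and will then be crossed over to receive 7 days of the other treatment". That is the only washout mentioned. The same section calls Phase 1 a 5-week crossover. Phase 2 comes once both 7-day studies are done: "subjects will then be treated with LOR 10 mg bid (n= 40) for 24 weeks". No interval, washout or new baseline visit is stated between the phases. The Scientific Abstract describes the same step as "subjects will then be continued on lorcaserin (n= 40) for 24 wks".

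On body weight, the Study Design section says of Phase 1: "Subjects will continue on a weight maintenance diet during this time to remain weight stable". In Phase 2, all subjects are counselled to "reduce their daily caloric intake to 600 kcal below their calculated caloric requirement".

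The Statistical Procedures section says: "Multiple regression modeling will be used to predict phase 2 wt loss in the LOR-treated participants from the within-subject difference". The difference meant is the one in test-meal results, and CSF POMC from Phase 1 is used as well. The section does not say which visit's weight is the starting point for Phase 2 weight loss, and it names no sequence or period term. It also plans stepwise regression for the wider set of associations.

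**The concern.** Predicting 24-week weight loss from the Phase 1 response is the main purpose of the trial. It is also the reason given for recruiting 40 subjects when the Phase 1 comparison needs only 24. The outcome of that model should therefore be measured in the same way in every subject.

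Read as written, it may not be. In the LOR-second sequence (placebo, then LOR), a weight taken at the start of Phase 2 comes after a week on drug. In the LOR-first sequence it comes after four weeks off drug. If LOR lowers weight in its first week, that loss falls before the Phase 2 baseline in one sequence. In the other it may have been regained by then.

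Sequence is randomised, so on its own this only adds noise to the outcome. It becomes a bias if the predictor also depends on sequence, which a period effect would cause. Suppose subjects eat more, or less, at their second test meal whatever the drug. That shift then enters the LOR-minus-placebo difference with one sign in LOR-second subjects and the opposite sign in LOR-first subjects. Predictor and outcome would share a sequence component unrelated to the biology under study.

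**Working it through.** **The plan's own figures.** Phase 1 is 1 + 3 + 1 = 5 weeks, as stated, which leaves no room for a second washout. Recruitment is 32 / (1 − 0.20) = 40, as stated.

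**Time on and off LOR, assuming no gap between the phases:**

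| | LOR first | LOR second |
|---|---|---|
| Days off LOR just before Phase 2 | 21 + 7 = 28 | 0 |
| LOR days in Phase 1 | 7 | 7 |
| LOR days in Phase 2 | 24 × 7 = 168 | 168 |
| Total LOR days | 175 | 175 |

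The asymmetry concerns 7 days, which is 7/168 = 4.2% of the length of Phase 2.

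**Inputs for the size of the effect.** The documents give none of these, so all are assumptions:
- d, the difference between sequences in mean measured weight loss: 0.5 to 1.0 kg. This is towards the high side, given the maintenance diet.
- s, the SD of 24-week weight loss within a sequence: 5 kg.
- k, the period effect on the LOR-minus-placebo predictor, in units of that predictor's SD: 0.5. It enters as +k in one sequence and −k in the other.
- Sequences of equal size.

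**Induced correlation when predictor and outcome are truly unrelated:**

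r = [k / √(1 + k²)] × [(d/2) / √(s² + d²/4)]

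- d = 0.5, s = 5, k = 0.5: 0.447 × (0.25 / 5.006) = 0.022.
- d = 1.0, s = 5, k = 0.5: 0.447 × (0.5 / 5.025) = 0.044.
- Extreme case, d = 2, s = 4, k = 0.5: 0.447 × (1 / 4.123) = 0.108.
- With k = 0, r = 0.

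**A check on the SD from the documents.** The Study Purpose and Rationale section reports that 47% of drug-treated subjects lost at least 5% of body weight and 22% lost at least 10%. It does not give the follow-up time. Under a normal distribution these points lie at z = 0.075 and z = 0.772. The SD is then 5 / (0.772 − 0.075), about 7.2 percentage points, and the mean is 5 − 0.075 × 7.2, about 4.5%. With d = 0.5 to 1.0 percentage points and this SD, r is 0.016 to 0.031. Over d = 0.25 to 2.0, s = 4 to 7.2 and k = 0.3 to 0.5, r runs from 0.005 to 0.108.

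**Comparison with the significance threshold.** With 32 subjects, the two-sided 5% critical value is r = t / √(t² + 30) with t = 2.042, which is 0.349. On the Fisher z scale, r = 0.044 shifts the test statistic by 0.044 × √29 = 0.24. The error rate becomes P(Z > 1.72) + P(Z < −2.20), about 5.6%. The extreme case shifts it by 0.109 × √29 = 0.59, giving P(Z > 1.37) + P(Z < −2.55), about 9%.

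**Noise alone, without a period effect.** A true correlation is multiplied by s / √(s² + d²/4). This is 0.999 at d = 0.5 and 0.995 at d = 1.0 with s = 5, and 0.970 in the extreme case.

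**The case against.** The case for leaving the plan alone has five parts.

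- **The missing gap is inferred from silence.** No text says that Phase 2 starts the next day. The Study Design section cites a figure that was not in the text available for this review and that might show an interval. This stands, and it is why the point is put as how the plan reads. The 5-week length and the abstract's word *continued* both favour no gap.
- **A difference in starting weight is assumed.** Phase 1 is meant to be weight-stable, and no Phase 1 weights are given. This stands.
- **Stronger readings go too far.** A reader might infer that drug exposure differs by sequence, or that 24-week weight loss is a different quantity in the two halves. Total LOR is equal, and both sequences receive 24 weeks of LOR with the same calorie target in Phase 2. A reader might also infer that mean loss or the number of 5% responders is understated. The Statistical Procedures section plans neither analysis; it uses weight loss in correlations and regressions.
- **The effect is small.** It also needs two assumptions at once, a weight shift and a period effect. This stands.
- **Moving the primary baseline to the weight before the first dose has its own costs.** It replaces the plan's named outcome and puts the LOR week, in which the predictor is measured, inside the outcome. It also compares 25 continuous weeks in one sequence with 1 + 24 interrupted weeks in the other. This stands, so that baseline belongs in a sensitivity analysis.

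None of this is a reason to omit the sequence term or to leave the baseline visit undefined.

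**Conclusion.** The point holds as a modest omission. As written, the sequences enter Phase 2 after 28 and 0 days off LOR, with equal total LOR. The prediction model has no sequence term, and its outcome has no stated starting weight. The induced correlation is about 0.02 to 0.04 under the assumed values and about 0.11 at the extreme, against a critical value of 0.349. It would not create or overturn a clear result. It rests on there being no gap between the phases, on some weight change in the LOR week despite the maintenance diet, and on a period effect in the predictor. It also takes all subjects to receive LOR in Phase 2, as the (n= 40) statement says, although the opening sentence of that part of the Study Design section mentions LOR or placebo. The change is worth making because it uses a factor the trial already randomises and costs almost nothing.

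**What to change.** In the Statistical Procedures section:

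1. Include randomised sequence as a fixed covariate in the regression predicting Phase 2 weight loss. Keep it in the model whatever its p-value, outside any stepwise selection. This removes the mean sequence shift in the outcome and the period effect in the predictor together.
2. Keep change from the start of Phase 2 as the named outcome, and state which visit's weight starts it.
3. Report percent change from the weight before the first Phase 1 dose to week 24 as a sensitivity analysis. This also covers something a sequence term cannot: in the LOR-second sequence, the strongest acute responders may lose the most weight before the Phase 2 baseline.

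In the Study Design section and the Scientific Abstract, reconcile *treated* with *continued* and state the interval between period 2 and Phase 2. The interval itself is for the sponsor to decide; the analysis only needs it to be stated.

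The cost is one degree of freedom (for example, residual degrees of freedom fall from 29 to 28 with 32 subjects, an intercept and two predictors), plus one weight before the first dose if it is not already recorded. No subjects or visits are added, and treatment does not change.
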